10.6.2.4. Prior and Concomitant Medications

Prior and Concomitant Medications

Non-randomized ESA use during treatment period

- Subjects will be considered to have non-randomized ESA use during the treatment period if they have any ESA concomitant medication records with one of the following two reasons for medication:
 - o Non-randomized ESA treatment in addition to randomized treatment
 - Non-randomized ESA treatment instead of randomized treatment

Duration of non-randomized ESA use during treatment period

- If there is only one concomitant medication record of non-randomized ESA use during the treatment period, then:
 - Duration (days) = earliest of (concomitant medication record end date, last nonzero dose date + 1 day) – latest of (concomitant medication start date, treatment start date) + 1 day
- If there are multiple concomitant medication records of non-randomized ESA use during the treatment period, then the duration of non-randomized ESA use will add the durations for all records, subtracting any overlapping days that may exist between the multiple records.

Clopidogrel start date for new clopidogrel users

 New clopidogrel users are subjects who did not use clopidogrel on randomization day, but started their clopidogrel use after randomization during the on-treatment state for concomitant medications. To determine the start date of clopidogrel for the new users, only the first clopidogrel record during the on-treatment state for concomitant medications will be considered. The start date will be the first day subjects on both clopidogrel and randomized treatment.

200807

10.6.2.5. Exposure and Compliance

Exposure and	Compliance					
Exposure						
	days) = Treatment st	op date – treatment s	start d	ate + 1 day		
Compliance						
eCRF g date, a date fo stop da • A comp accordi hold/ze	bages and will only b nd will not be calcula r subjects who have ate. bliance category will l ing to the following ta pro-dose as assigned	ed based on data rec e calculated for subjected after a subject's t a non-missing treatm be assigned to each t ables. Exposure recor by the IRT will be cated e records will be cated	ects w reatm ent st rando rds co tegori	ith a non-missing ent stop date, of art date and a m mized treatment rresponding to p ized in the comp	g treati r study hissing expos periods liant ca	ment start conclusion treatment sure record of dose ategory and
	Under Compliant	Compliant		Over Compliant		
	Compliance for the exposure record < 80%	Compliance for the exposure record $\frac{2}{80\%}$ and $\leq 120\%$	≥	Compliance for exposure record 120%		
	Where compliance for the exposure record is calculated as 100% * [# dispensed – (# returned + # lost)] / # tablets per day / (dose stop date – dose start date +1)					
	 # tablets per day: 1 tablet per day: 1n 2 tablets per day: 1 3 tablets per day: 2 	• •	3mg, 1	l0mg		
0	rhEPO Everv 4 We	ek Exposure Records	: Bas	ed on Number o	f Dose	es Given
D	uration of xposure Record	Under Compliant	1	npliant		Compliant
	– 14 days	< 1 dose	1 do	ose	> 1 d	ose
1	5 – 42 days	< 1 dose	1 or	2 doses	> 2 d	oses
43	3 – 70 days	< 2 doses	2 or	⁻ 3 doses	> 3 d	oses
71 – 98 days		< 3 doses	3 or	· 4 doses	> 4 doses	
9	9 – 126 days	< 4 doses	4 or	5 doses	> 5 d	oses
E	tc.					
0	rhEPO Every 2 We	ek Exposure Records	s: Bas	ed on Number o	f Dose	es Given
D	uration of xposure Record	Under Compliant		npliant		Compliant
1	– 7 days	< 1 dose	1 do	ose	> 1 d	ose

200807

8 – 21 days	< 1 dose	1 or 2 doses	> 2 doses
22 – 35 days	< 2 doses	2 or 3 doses	> 3 doses
36 – 49 days	< 3 doses	3 or 4 doses	> 4 doses
50 – 63 days	< 4 doses	4 or 5 doses	> 5 doses
64 – 77 days	< 5 doses	5 or 6 doses	> 6 doses
78 – 91 days	< 6 doses	6 or 7 doses	> 7 doses
92 – 105 days	< 7 doses	7 or 8 doses	> 8 doses
Etc.			
	eek Exposure Records	Based on Number of	
Duration of Exposure Record	Under Compliant	Compliant	Over Compliant
1 – 3 days	< 1 dose	1 dose	> 1 dose
4 – 10 days	< 1 dose	1 or 2 doses	> 2 doses
11 days	< 1 dose	1 or 2 or 3 doses	> 3 doses
12 – 17 days	< 2 doses	2 or 3 doses	> 3 doses
18 days	< 2 doses	2 or 3 or 4 doses	> 4 doses
19 – 24 days	< 3 doses	3 or 4 doses	> 4 doses
25 days	< 3 doses	3 or 4 or 5 doses	> 5 doses
26 – 31 days	< 4 doses	4 or 5 doses	> 5 doses
32 days	< 4 doses	4 or 5 or 6 doses	> 6 doses
33 – 38 days	< 5 doses	5 or 6 doses	> 6 doses
39 days	< 5 doses	5 or 6 or 7 doses	> 7 doses
40 – 45 days	< 6 doses	6 or 7 doses	> 7 doses
46 days	< 6 doses	6 or 7 or 8 doses	> 8 doses
47 – 52 days	< 7 doses	7 or 8 doses	> 8 doses
53 days	< 7 doses	7 or 8 or 9 doses	> 9 doses
Etc.			
•	osure Records: Based	on Number of Doses (
Duration of Exposure Record	Under Compliant	Compliant	Over Compliant
1 – 2 days	< 1 dose	1 dose	> 1 dose
3 – 4 days	< 1 dose	1 or 2 doses	> 2 doses
5 – 6 days	< 2 doses	2 or 3 doses	> 3 doses
7 days	< 2 doses	2 or 3 or 4 doses	> 4 doses
8 – 9 days	< 3 doses	3 or 4 doses	> 4 doses
10 – 11 days	< 4 doses	4 or 5 doses	> 5 doses
10 10 days		– – –	

5 or 6 doses

5 or 6 or 7 doses

> 6 doses

> 7 doses

< 5 doses

< 5 doses

12 – 13 days

14 days

200807

Exposure and Compliance					
	15 – 16 days	< 6 doses	6 or 7 doses	> 7 doses	
	17 – 18 days	< 7 doses	7 or 8 doses	> 8 doses	
	19 – 20 days	< 8 doses	8 or 9 doses	> 9 doses	
	21 days	< 8 doses	8 or 9 or 10 doses	> 10 doses	
	Etc.				

- Compliance will be summarized for the following time periods: Day 1 < Week 28, Week 28 < Week 52, Week 28 < End of Treatment, and Day 1 < End of Treatment (Overall compliance).
- Within each period, the percentage of time that a subject spent in each of the 3 categories above or with missing compliance data will be determined and will be based on the durations of each record within the period.
- A subject's compliance category will be the category that corresponds to the highest percentage of total time. In the unlikely event of a tie, the lower compliance category will be chosen (i.e., in a tie between under and compliant, under is chosen; in a tie between compliant and over, compliant is chosen; and in a tie between under and over, under is chosen; in a tie with missing, missing is chosen).

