10.1. Appendix 1: Protocol Deviation Management and Definitions for Per-Protocol Population

10.1.1. Exclusions from Per-Protocol Population

Exclusions from the PP population include events that, if they should occur, might:

- Directly impact the hemoglobin efficacy endpoint; or
- Lead to permanent discontinuation of study treatment or study withdrawal and hence indirectly impact the efficacy endpoint by causing data to be missing.

The following criteria define the events which, if they occur prior to the end of the EP, may lead to exclusion of a subject from the PP population. Exclusions from the PP Population will be subject to blinded review by the study team. The study team will also review the listing of unique concomitant medication terms to identify the prohibited medications. These reviews will occur before database has been unblinded for analysis.

A subject meeting any of the following criteria may be excluded from the Per-Protocol population:

Number	Exclusion Description
01	Baseline HemoCue Hgb value outside of Randomization (Day 1) Hgb entry criteria range
02	Less than 5 out of 7 scheduled evaluable ¹ Hgb values ² from the EP
03	Non-compliance with randomized treatment (compliance category of under compliant or over compliant) during the EP, based on eCRF randomized medication exposure and compliance forms
04	Inadequate iron status during EP, defined as ferritin \leq 100 ng/mL on two consecutive scheduled visits or TSAT \leq 20% on two consecutive scheduled visits
05	Subject received prohibited medication ³ for more than two weeks during EP

NOTES:

1. See Section 10.6.3.

2. Based on central laboratory Hgb values. If central laboratory Hgb value is missing, a non-missing HemoCue Hgb value will be used.

 Prohibited medications include strong inhibitors of CYP2C8 (e.g., gemfibrozil) and strong inducers of CYP2C8 (e.g., rifampin/rifampicin).

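### Compliance is graded by percentage for daprodustat and by whole-dose windows for rhEPO, so equal adherence can get different labels by arm, and the label feeds per-protocol criterion 03

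*SAP*

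**What the plan says.** Section 10.6.2.5 (Exposure and Compliance) assigns a category to each exposure record.

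- **Daprodustat:** a percentage. Tablets dispensed, less those returned or lost, are divided by the number expected, through "tablets per day / (dose stop date – dose start date +1"). Under compliant is "Compliance for the exposure record < 80"%, and compliant runs from 80% to 120%. The over-compliant limit is read here as above 120%.
- **rhEPO:** separate tables of doses given for every-4-week, every-2-week, weekly and three-times-weekly dosing, indexed by record length in days. Most rows accept two adjacent counts, as in the weekly row "47 – 52 days < 7 doses 7 or 8 doses > 8 doses" and the three-times-weekly row "19 – 20 days < 8 doses 8 or 9 doses > 9 doses". A three-count window appears only at isolated lengths, such as "53 days < 7 doses 7 or 8 or 9 doses > 9 doses". Each table ends in an open continuation.
- **Subject level:** "A subject's compliance category will be the category that corresponds to the highest percentage of total time", with dose-hold records counted as compliant.

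Section 6.2.6 tabulates these categories, and the time spent in each, by treatment group. Section 10.1.1 lists as per-protocol criterion 03 "Non-compliance with randomized treatment (compliance category of under compliant or over compliant) during the EP". A subject who meets a criterion may be excluded, after blinded review. Section 7.1.2.5 uses the per-protocol population for a supportive Hgb analysis.

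**The concern.** The two rules answer different questions. One asks what fraction of the expected amount was taken; the other asks whether the count falls in a narrow window around the expected number. They need not agree at the same adherence, and the SAP does not reconcile them. A difference between arms in the share of under- or over-compliant subjects could then reflect the grading rule and not behaviour.

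The per-protocol link makes this more than a display matter. In a non-inferiority comparison the per-protocol analysis is a check on the ITT result. It does that job best when both arms are selected by one rule. Here, who is flagged under criterion 03 depends partly on the arm and, within rhEPO, on dosing frequency and record length.

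**Working it through.** **Inputs.** The daprodustat limits and all rhEPO rows come from section 10.6.2.5. Dispensing every 4±1 weeks is in footnote 17 to the schedule in Appendix 2. Section 10.6.3.6 has sites open an exposure record at each IRT dosing instruction, except when the same treatment is re-dispensed.

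**Reproducing the table.** For a weekly record of D days, minimum = max(1, floor((D+2)/7)) and maximum = max(1, floor((D−4)/7)+2) give every printed weekly row from 1 to 53 days. At D = 47 to 52 the result is 7 to 8, as printed.

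**Converting counts to percentages.** Percentage = 100 × doses given / (D / dosing interval).

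| rhEPO record | Expected | Given | % | rhEPO label | 80–120% label |
|---|---|---|---|---|---|
| Weekly, 35 days | 35/7 = 5 | 4 | 80.0 | Under | Compliant |
| Weekly, 49 days | 49/7 = 7 | 6 | 85.7 | Under | Compliant |
| 3×/week, 19 days | 19×3/7 = 8.14 | 7 | 86.0 | Under | Compliant |
| Every 4 weeks, 42 days | 42/28 = 1.5 | 1 | 66.7 | Compliant | Under |
| Every 4 weeks, 28 days | 28/28 = 1 | 2 | 200 | Compliant | Over |
| Weekly, 28 days | 28/7 = 4 | 3 | 75.0 | Under | Under |

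Across the whole 47 to 52 day row, 6 doses is 89.4% down to 80.8% of expected, and is under compliant at every length.

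**All printed combinations of length and count.**

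| | Weekly | 3×/week | Every 2 weeks | Every 4 weeks |
|---|---|---|---|---|
| Under on rhEPO, inside 80–120% | 14 | 3 | 34 | 7 |
| Compliant on rhEPO, below 80% | 4 | 5 | 4 | 7 |

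These are cells of the tables, not frequencies of patients. They show that the mismatch runs both ways. The rules agree on shortfalls in 28-day weekly records. They agree fully in three-times-weekly records of 14 days (5 to 7 of 6 expected) and 21 days (8 to 10 of 9): 4/6 = 67%, 8/6 = 133%, 7/9 = 78% and 11/9 = 122% fail under both.

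**Illustration only.** Assume each scheduled dose or tablet-day is taken independently with probability 0.90 in both arms. The probability that a record is under compliant is then:

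| Record | rhEPO, SAP rule | Daprodustat | rhEPO, 80% rule |
|---|---|---|---|
| Weekly, 35 days | P(X≤4 of 5) = 1−0.9⁵ = 41% | P(X≤27 of 35) = 2% | P(X≤3 of 5) = 8% |
| Weekly, 49 days | P(X≤6 of 7) = 1−0.9⁷ = 52% | P(X≤39 of 49) = 2% | P(X≤5 of 7) = 15% |
| 3×/week, 28 days | P(X≤10 of 12) = 34% | P(X≤22 of 28) = 5.5% | P(X≤9 of 12) = 11% |

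At probability 0.85 the last row gives 56% for rhEPO against 24% for daprodustat. That row is not printed: it assumes the pattern 5–7 at 14 days and 8–10 at 21 days continues to 11–13 at 28 days.

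**The case against.** Whole-dose windows have a sound reason. Record boundaries cut across infrequent dosing, and a strict percentage on one or two expected doses is unstable. The two arms also measure different things: tablets not returned, against doses recorded as given. Different rules are defensible as a starting point, and they were specified in advance.

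A reader might infer that rhEPO subjects are graded more strictly overall, so that the per-protocol set loses more of them. The SAP does not support that. rhEPO is stricter in many longer records and looser in short or sparse ones, and at several common lengths the rules agree. The 49-day example lies outside the 4±1 week dispensing interval; it needs re-dispensing of an unchanged treatment to arise, and the SAP gives no frequency for that. The 35-day example lies inside the interval.

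Nor do the record-level percentages translate into exclusion rates. The subject's label is the category with most time in the EP, dose holds count as compliant, and a flagged subject is only a candidate for exclusion. Part of the modelled gap is granularity: with 80% applied to both arms, 8% to 15% of the rhEPO records would still be under compliant, against 2% to 5.5% on daprodustat.

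These objections limit size and direction. They do not remove the inconsistency. Blinded review does not cure it either, because the flag put before the reviewers already comes from a different rule in each arm.

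**Conclusion.** The inconsistency is real and can be read directly from the printed tables. The same percentage adherence can be compliant in one arm and under or over compliant in the other, and criterion 03 uses the result. By-arm compliance tables should not be compared as they stand, and the supportive per-protocol Hgb analysis draws its population by unequal rules.

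The consequence is limited. The co-primary Hgb and MACE analyses are ITT and unaffected. The net direction is not fixed, and the number of subjects affected cannot be derived from the SAP. The record-level conflicts need only the printed rows and the dosing interval. The probabilities also rest on independent adherence at an assumed, equal rate and, for the 28-day three-times-weekly record, on continuing the table. The point is worth correcting before unblinding because the correction is cheap, not because a conclusion of the trial hangs on it.

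**What to change.** For the subject-level category in each summary period of section 6.2.6, and for criterion 03 over the EP:

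1. Take all exposure records in the period that are not dose holds.
2. Sum the doses or tablets given, and the doses or tablets expected from each record's length and frequency.
3. Divide given by expected and apply the same 80% to 120% limits once per subject, in both arms.

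Pooling deals with most of the boundary problem that the dose windows were meant to solve. Over Weeks 28 to 52 (168 days) without holds, expected rhEPO doses are 6 on every-4-week dosing, 24 weekly and 72 three times weekly. Even in the sparsest case 5/6 = 83% is compliant and 4/6 = 67% is not.

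Do not add a per-record allowance of one dose either way: with one dose expected in a 28-day record, it would call zero doses compliant. If the table of time in each category is kept record by record, footnote it as not comparable between arms.

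The cost is SAP wording and some reprogramming, with no new data. rhEPO will remain coarser than daily tablets because it has fewer expected doses, most visibly in subjects with short follow-up in a period.

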10.6.3. Efficacy

10.6.3.1. Hemoglobin Endpoints

Не	moglobin Values		
Ce	ntral Laboratory and HemoCue Hgb Values		
•	 When source of Hgb measurement is not specified: For reporting purposes, central laboratory Hgb values will be used, unless otherwise specified. However, if a central laboratory Hgb value is missing, a corresponding non-missing HemoCue Hgb value will be used. This approach will be used for the co-primary Hgb analysis. 		
•	Some displays may be created for either central laboratory Hgb values only or HemoCue Hgb values only. The central laboratory summary will be considered the primary summary in this case.		
Ev	aluable Hemoglobin Values		
•	Evaluable Hgb values are on-treatment Hgb values (see Section 10.4.1) that are not taken within the 8 weeks following a red blood cell transfusion, a whole blood transfusion, or a non- randomized ESA treatment which occurs on or after the randomization date. Red blood cell transfusions, whole blood transfusions and non-randomized ESA treatments occurring on or after the randomization date are identified by comparing the start and stop date of the respective transfusion or ESA concomitant medication record to the randomization date.		
Im	Imputed Hemoglobin Values		
•	For each missing value between baseline to Week 52 (inclusive), 200 imputed values will be generated using the multiple imputation method (see Section 7.1.2). The average of these 200 imputed values will be used as the value for this missing value in the summary tables and figures.		

He	emoglobin V	alues				
•	For co-primary efficacy Hgb analysis and the corresponding subgroup analyses using all available observed and imputed Hgb values (on and off-treatment), Rubin's rules [Rubin, 1987] will be used to combine results of the imputed datasets using SAS PROC MIANALYZE procedure.					
EF	[•] Hemoglobi	n Value for Co	p-primary Hg	b Analysis		
•	(See Section during this Should the	on 10.6.1) inclu time period. assessment da	ding any impu ates for Hgb v	uted and unsch alues from the	treatment) Hgb values neduled Hgb values that Early Treatment Disco	t were taken ntinuation visit
					e values will be include ot be included in the EF	
EF	-	-			ble Hgb Supportive Ar	
•	For each su including an Should the and the En	ubject, the meany evaluable ur assessment da d of Study visit	n of all evalua nscheduled H ates for Hgb v fall within the	able Hgb value gb values that alues from the EP, then thes	es during the EP (See S were taken during this Early Treatment Disco e values will be include	ection 10.6.1) time period. ntinuation visit d as unscheduled
	-				ot be included in the EF	^o mean.
EF	•	n Value for Al			2	
•	 For each subject, the mean of all Hgb values during the Alt. EP (See Section 10.6.1) including any imputed and unscheduled Hgb values that were taken during this time period. This analysis will be conducted using all available (on and off treatment) Hgb values and separately using evaluable Hgb values only. Should the assessment dates for Hgb values from the Early Treatment Discontinuation visit and the End of Study visit fall within the Alt. EP, then these values will be included as unscheduled Hgb values. Hgb values from the Follow-up visit will not be included in the Alt. EP 					
	mean.					
Us	se of Unsche	duled Hemog	lobin Values	and Multiple	Hgb Values on the Sa	me Date
•						
	co-primary Hgb analysis, where central lab values are used if they are available and if the central lab value is missing, then a corresponding non-missing HemoCue Hgb value is used.					
•		ning scenarios i /pe apply to all	-		heduled and unschedu	led Hgb values of
	Scheduled Central Lab Hgb Value	Unscheduled Central Lab Hgb Value	Scheduled HemoCue Hgb Value	Unscheduled HemoCue Hgb Value	Value to Use	Type/Label
	X				Scheduled central lab Hgb value	Scheduled visit
		х			Unscheduled central lab Hgb value	Unscheduled
			х		Scheduled HemoCue	Scheduled visit
					Hgb value Average of scheduled	

200807

			х	Unscheduled HemoCue Hgb value	Unscheduled	
	multiple			Average of unscheduled central lab Hgb values	Unscheduled	
			multiple	Average of unscheduled HemoCue Hgb values	Unscheduled	
х	x			Average of central lab Hgb values	Scheduled visit	
х		Х		Scheduled central lab Hgb value	Scheduled visit	
Х			х	Scheduled central lab Hgb value	Scheduled visit	
	х	Х		Unscheduled central lab Hgb value	Unscheduled	
	x		х	Unscheduled central lab Hgb value	Unscheduled	
		X	x	Average of HemoCue Hgb values	Scheduled visit	

Time In Range

Time in Range During the EP

- Number of days that a subject's evaluable Hgb is within the analysis range of 10-11.5 g/dL inclusive during the EP (See Section 10.6.1), including any unscheduled evaluable Hgb values that were taken during this time period.
- Use of unscheduled Hgb values follows the scenarios for unscheduled and multiple Hgb values.
- Linear interpolation is used to estimate Hgb between visits, accounting for any intermittent missing values (Rosendall, 1993).

Percent Time in Range During the EP

- Time in Range During the EP / [Earlier of (Date of the last evaluable Hgb value, Week 52 visit date) Later of (Date of the first evaluable Hgb value that between Week 16 and Week 52 inclusive, Week 28 visit date)]
- Note: Percent time in/below/above range during the EP is only defined for subjects with a
 Treatment Stop Date that is on or after their Week 28 visit date, and have at least two
 evaluable Hgb values on different days, where at least one evaluable Hgb value is contained
 within the EP and another evaluable Hgb value occurs within the range of the Week 16 visit
 through 4 weeks following the Week 52 visit, inclusive.

Time in Range During the MP

- Number of days that a subject's evaluable Hgb is within the analysis range of 10-11.5 g/dL inclusive between Weeks 28 and End of Study inclusive, including any unscheduled evaluable Hgb values that were taken during this time period.
- Linear interpolation is used to estimate Hgb between visits, accounting for any intermittent missing values (Rosendall, 1993).

Percent Time in Range During the MP

• Time in Range During the MP / [Earlier of (Date of the last evaluable Hgb value, End of study date)– Later of (Date of the first evaluable Hgb value that is on or after week 16, Week 28 visit

200807

Time In Range

date)]

Note: Percent time in/below/above range during the MP is only defined for subjects with a
Treatment Stop Date that is on or after their Week 28 visit date, and have at least two
evaluable Hgb values on different days, where at least one evaluable Hgb value is contained
within the MP and another evaluable Hgb value occurs within the range of the Week 16 visit
through the Treatment Stop Date + 1 day.

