• All available observed Hgb values (on and off-treatment) will be summarized using mean, standard deviation, minimum, P25, median, P75 and maximum at each visit by treatment group. In addition to scheduled visits, the baseline value and mean MP, mean EP, mean Alt EP, and end of treatment values will be included (see Section 10.6.3). This summary is repeated by dialysis type at randomization.
• This summary of Hgb will also be repeated for visits up to and including Week 52,

200807

Hgb Efficacy Co-Primary Statistical Analyses

using the data used for the primary Hgb analysis (i.e., including imputed values). (see Section 10.6.3)), and by dialysis type at randomization.

- All available observed Hgb change from baseline values (on and off-treatment) will also be summarized using mean, standard deviation, minimum, P25, median, P75, and maximum at each post-baseline visit, including the mean MP, mean EP, mean Alt EP, and end of treatment values (see Section 10.6.3). This summary is repeated by dialysis type at randomization.
 - This summary of Hgb will also be repeated for visits up to and including Week 52, using the data used for the primary Hgb analysis (i.e., including imputed values). (see Section 10.6.3)), and by dialysis type at randomization.

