- The number and percentage of subjects with imputed data in the primary Hgb analysis will be provided by treatment group. The number and percentage of subjects by reason for data imputation will be provided. Reasons include: intermittent missing Hgb values, death before Week 28, death during Week 28 – 52, investigator site closed before Week 28, investigator site closed during Weeks 28-52, lost to follow-up before Week 28, lost to follow-up during Week 28 - 52, consent withdrawn before Week 28, consent withdrawn during Week 28 - 52, and other monotone missing Hgb values. Subjects will be further classified as either having observed all 7 scheduled EP Hgb values, having observed a partial schedule of EP Hgb values, having observed no scheduled EP Hgb values with at least one unscheduled EP Hgb value, or having observed no EP Hgb values, scheduled or unscheduled. For subjects with partial scheduled EP Hgb values, both the pattern of imputed data (intermittent, monotone) and the amount of imputed data (1 – 6 scheduled Hgb values missing) will be summarized. For subjects with partial scheduled EP Hgb values and a monotone imputed data pattern, the reason for the monotone imputed scheduled EP Hgb values will be provided. Reasons include: death during Week 28-52, investigator site closed during Weeks 28-52, lost to follow-up during Week 28 – 52, consent withdrawn during Week 28 – 52, and other monotone imputed Hgb values. And for summaries of the amount of missing scheduled EP Hgb values, the presence or absence of additional unscheduled EP Hgb values will be summarized.
- The least square (LS) mean estimates and standard errors by treatment group, LS mean difference, two-sided 95% CI and one-sided non-inferiority p-value for the difference in the coprimary Hgb endpoint between the daprodustat and rhEPO arms from the ANCOVA model will be presented. The number of subjects contributing to the analysis and the associated mean and standard deviation of the baseline and EP Hgb values will also be displayed with the results of the ANCOVA model.
- The LS mean difference and associated two-sided 95% CI will be displayed on a forest plot together with supportive analysis results (excluding the Tipping Point Analysis).

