- All available observed Hgb values (on and off-treatment (see Section 10.6.3)) will be displayed graphically for each scheduled study visit using a line plot. The line plot of mean values and 95% CIs by time will include horizontal reference lines to depict the Hgb analysis range (10-11.5 g/dL), vertical reference lines to identify the EP (weeks 28-52), and the number of subjects by treatment group contributing to each mean value. The plot will be repeated by dialysis type at randomization.
 - This figure will also be repeated for visits up to and including Week 52, using the data used for the primary Hgb analysis (i.e., including imputed values). (see Section 10.6.3)).
- All available observed Hgb change from baseline values (on and off-treatment (see Section 10.6.3)) will be displayed graphically for each scheduled study visit using a line plot. The line

200807

Hgb Efficacy Co-Primary Statistical Analyses

plot of mean values and 95% CIs by time will include vertical reference lines to identify the EP (Weeks 28-52), and the number of subjects by treatment group contributing to each mean value. The plot will be repeated by dialysis type at randomization.

- This figure will also be repeated for visits up to and including Week 52, using the data used for the primary Hgb analysis (i.e., including imputed values). (see Section 10.6.3)).
- A listing of all hemoglobin values will be provided, including treatment, most recent dose, site ID, unique subject ID, visit, assessment date, select demographic information and central laboratory and HemoCue Hgb values.

Model Results Interpretation

• Non-inferiority will be achieved if the lower limit of the two-sided 95% CI of the treatment difference is greater than the pre-specified non-inferiority margin of -0.75 g/dL.

Sensitivity Statistical Analyses

Tipping Point (Multiple Imputation) Analysis

- Tipping point analysis will be performed using all available Hgb values (on and off-treatment) as a sensitivity for the co-primary estimand.
- Tipping point analyses will be conducted under a range of missing data assumptions to determine how extreme assumptions need to be for non-inferiority conclusions to change. Assumptions about missing Hgb values on the daprodustat and rhEPO arms will vary independently and will include scenarios where subjects with missing data on daprodustat have worse outcomes than subjects with missing data on rhEPO.

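### By-visit Hgb tables and plots that include imputed values replace each missing value by the mean of its 200 imputations, so their SDs and 95% CIs are too small

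*SAP*

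**What the plan says.** SAP Section 10.6.3.1 (Imputed Hemoglobin Values) generates 200 imputations for each missing Hgb through Week 52. It then sets the display rule: "The average of these 200 imputed values will be used as the value for this missing value in the summary tables and figures". The next item there assigns Rubin's rules to the co-primary Hgb analysis and its subgroup analyses. It does not assign them to the displays.

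Section 7.1.2.5 (Model Results Presentation) defines the displays, first on observed values:

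- Tables: Hgb "will be summarized using mean, standard deviation, minimum, P25, median, P75 and maximum at each visit by treatment group", with a matching table for change from baseline. Both are repeated through Week 52 on the primary-analysis data, imputed values included.
- Plots: "The line plot of mean values and 95% CIs by time will include horizontal reference lines to depict the Hgb analysis range", with the number of contributing subjects shown, and a similar plot for change from baseline. For each, "This figure will also be repeated for visits up to and including Week 52, using the data used for the primary Hgb analysis".

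No section adjusts the SD, quartiles or CI in the imputed-data versions for the fact that some values were imputed.

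**The concern.** The mean of 200 draws for one missing value is close to its conditional mean given the subject's other data. Averaging removes the residual scatter that a real measurement would have, and also the variation between imputations that carries the uncertainty of the imputation model. The averaged value then enters the visit SD and CI as if it had been measured.

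The result runs the wrong way: the more data are lost at a visit, the tighter the error bars. They become narrower than they would be with nobody missing.

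Some missingness is built into the schedule. Section 10.2.1.3 gives subjects who permanently stop randomized treatment visits at Weeks 4, 16, 28, 40 and 52 in year 1, whereas Section 7.1.2.5 counts seven scheduled values per subject in the evaluation period. Weeks 32, 36, 44 and 48 will usually have to be imputed for these subjects. If discontinuation differs between arms, the shrinkage will differ too. At stake is the honesty of the intervals and spreads in these displays, not the trial's decision.

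**Working it through.** The SAP states no Hgb SD, missing fraction or CI width, so there is no figure of its own to reproduce. The check is on the rule itself.

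**Inputs**

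- From the SAP: 200 imputations, averaged for display (Section 10.6.3.1); SDs and 95% CIs by visit on those data, imputed values limited to 6–15 g/dL (Section 7.1.2.5).
- Assumed: missing fraction at a visit, m = 0.10 to 0.30; share of Hgb variance explained by the imputation model, R² = 0.1 to 0.5. For the absolute scale only: 1500 per arm and SD 1.0 g/dL.

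**Formulas** (SE in units of σ/√N)

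1. An averaged imputation has variance of about R²σ² instead of σ². Displayed SD / true SD = √(1 − m(1 − R²)). The plotted SE is the same quantity.
2. Valid multiple-imputation SE with many imputations = √((1 − R²)/(1 − m) + R²).
3. CI width ratio = (1)/(2). Coverage = 2Φ(1.96 × ratio) − 1.

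**Worked case, m = 0.2, R² = 0.3**

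- Plotted SE = √(1 − 0.2 × 0.7) = √0.86 = 0.927.
- Valid SE = √(0.7/0.8 + 0.3) = √1.175 = 1.084.
- Ratio = 0.927/1.084 = 0.856; coverage about 90.6%.
- For comparison, the complete-data SE is 1.000 and the observed-only SE is 1/√0.8 = 1.118. Beside the observed-only plot, the imputed version would look 17% tighter (0.927/1.118 = 0.83). The valid gain is 3% (1.084/1.118 = 0.97).

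**Range**

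| m | R² | SD ratio | CI width ratio | Coverage |
|---|---|---|---|---|
| 0.10 | 0.1 | 0.954 | 0.910 | 92.5% |
| 0.10 | 0.5 | 0.975 | 0.949 | 93.7% |
| 0.20 | 0.1 | 0.906 | 0.818 | 89.1% |
| 0.20 | 0.5 | 0.949 | 0.894 | 92.0% |
| 0.30 | 0.1 | 0.854 | 0.726 | 84.5% |
| 0.30 | 0.5 | 0.922 | 0.837 | 89.9% |

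**Simulation check** (proper regression imputation, 200 imputations, 1500 per arm, true SD 1.0, limits 6–15, R² = 0.3, 400 replicates)

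| m | SD, averaged rule | SD, within-imputation | CI width ratio | Coverage, averaged | Coverage, Rubin |
|---|---|---|---|---|---|
| 0.10 | 0.965 | 1.000 | 0.929 | 91.8% | 93.5% |
| 0.20 | 0.929 | 1.002 | 0.856 | 91.5% | 94.5% |
| 0.30 | 0.889 | 1.001 | 0.778 | 86.5% | 93.8% |

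SDs and width ratios agree with the formulas (0.964, 0.927 and 0.889 for the SD; 0.929, 0.856 and 0.780 for the width). With 400 replicates, simulated coverage carries a standard error of about 1 percentage point (√(0.95 × 0.05/400) = 0.011).

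**Absolute scale.** 1.96/√1500 = 0.0506 g/dL.

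- m = 0.2, R² = 0.3: half-width 0.927 × 0.0506 = 0.047 instead of 1.084 × 0.0506 = 0.055; difference 0.008 g/dL.
- Worst corner, m = 0.3, R² = 0.1: 0.854 × 0.0506 = 0.043 instead of 1.177 × 0.0506 = 0.060; difference about 0.016 g/dL.

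**The case against.** The strongest reply is that nothing inferential depends on these displays. The non-inferiority decision rests on the ANCOVA interval, which combines the 200 datasets by Rubin's rules. The imputed-data tables and plots are repeats of observed-data versions that are also planned, and Section 7.1.2.5 requires a detailed account by arm of how much was imputed and why. A shift of about 0.01 g/dL would hardly show on a plot with reference lines at 10 and 11.5 g/dL. All of this stands and limits the weight of the point. It does not make the rule right, because an interval labelled 95% should have that coverage.

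The size is also open to challenge. Off-treatment values are kept, and HemoCue fills in for a missing central value, so m may be low. The MCMC step for intermittent gaps uses later as well as earlier visits, so R² may be high. Both would bring the ratios closer to 1, but neither would reverse the direction.

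Several stronger readings are tempting, and the document does not support them:

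- That these are main efficacy displays. They are secondary repeats of the observed-data displays.
- That the plots would fail to match the ANCOVA because of this rule. The ANCOVA interval is for an adjusted difference in the mean over Weeks 28–52, so it differs from single-visit arm means under any imputation method.
- That the tabulated range shrinks. Observed extremes stay in the table, so averaging imputed values does not remove them.
- That the SD printed beside the ANCOVA is wrong. The SAP says "the associated mean and standard deviation of the baseline and EP Hgb values will also be displayed with the results of the ANCOVA model" but does not say whether that SD uses averaged values. It would be too small only if it does.

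**Conclusion.** The rule is wrong as written, within a narrow scope. In the imputed-data versions of the by-visit Hgb tables and the two line plots, SDs and 95% CIs are too small and P25/P75 are drawn inward whenever values are missing and the imputation model is imperfect. Across the assumed range (m 10–30%, R² 0.1–0.5), the SD is 85–98% of its true value, CI width about 73–95% of valid, and coverage about 84–94%. In absolute terms the half-width falls short by roughly 0.01 g/dL at the assumed 1500 per arm and SD of 1.0 g/dL. The direction is certain; the size rests on assumptions that the SAP does not supply.

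A reader might infer that the co-primary result is compromised. It is not: the estimate, CI, p-value and comparison with −0.75 g/dL use Rubin's rules. Visit means are essentially unbiased under the missing-at-random assumption of the imputation model, and observed-only displays are untouched.

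**What to change.** Delete the averaging sentence in Section 10.6.3.1. For every Hgb display that includes imputed values, state instead:

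- Mean and 95% CI: compute the visit mean and SE within each of the 200 datasets and combine by Rubin's rules.
- SD: square root of the average within-imputation variance.
- P25, median and P75: compute in each dataset and average over the 200.
- Minimum and maximum: observed values only. Taking them from the stacked imputations would fill the table with simulated extremes, up to the 6 and 15 g/dL limits, that no subject had.

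Say also that the evaluation-period SD shown with the ANCOVA follows the same rule.

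The cost is slightly wider error bars and a little programming. The 200 datasets already exist, PROC MIANALYZE is already in use for the ANCOVA, and no test, margin or estimate changes.
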